9.1.6.2. Height Velocity

Height will be collected 3 times per visit at the visits indicated in Section 2 using a stadiometer or other instrument of equivalent measuring capacity. Observed height velocity by gender and age group will be calculated at CCI [REDACTED], based on height measurements from the 3 to 12 months (preferably 4 to 6 months) preceding the study (from screening) or those obtained at baseline according to the following formula:

- $(\text{Present Height [cm]} - \text{Previous Height [cm]}) / \text{Interval (months) Between Measurements} \times 12$

Age-specific z-scores for height velocity by gender and age group will be calculated for each patient with reference to standard height velocity tables according to the following formula:

- $(\text{Observed Height Velocity [cm/y]} - \text{Mean Height Velocity for Age and Sex [cm/y]}) / (\text{Standard Deviation of the Mean})$

Full details on height velocity analyses can be found in the SAP.

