- Changed analysis approach for calculating confidence intervals in Section 6.1.3.
- Added language clarifying how missing data handling for continuous endpoints as well as modifications for missing data handling as part of the interim analysis (Section 6.3).
- Fixed categorical summary definitions for Bristol stool scale and at baseline in Table AMBU.6.3.
- Made the following changes to Table AMBU.6.4:
 - Updated definitions of MMS Clinical Remission, Alternate Clinical Remission, stool frequency (SF) component of clinical remission.
 - o Minor clarification of wording for Corticosteroid-free remission at Week 52
 - o For histology, added definitions for CCI , Histologic Remission, and histologic-endoscopic mucosal remission.
 - o For growth, added definitions for change from baseline (CFB) in height, CFB in weight, and height/weight z-scores and percentiles.
 - Removed definition of CCI
 - Added definition of EIM subcategory.
- Made the following changes to Table AMBU.6.5:

- Clarified missing data handling analysis methods for each endpoint variable (non-responder imputation [NRI], modified baseline observation carried forward (mBOCF), and as observed).
- Added the following secondary endpoints to be calculated: Pediatric Ulcerative Colitis Activity Index (PUCAI) CFB, Height CFB, Weight CFB, Histologic Remission, Histologic Improvement, and Histologic-Endoscopic Mucosal Remission, 30% improvement from baseline in Abdominal Pain.
- Clarified that Abdominal Pain will be summarized by age group.
- O Changed estradiol and testosterone level analyses to be change from baseline.
- Made the following changes to Table AMBU.6.6:
 - o Removed as part of the exploratory analyses.
 - o Clarified analyses that will be performed for alternate clinical remission.
 - Updated analysis method for Bristol Stool Scale.
 - Added missing data handling analysis methods for each endpoint variable (NRI, mBOCF, and as observed).
- Updated language in hepatic safety section (Section 6.13.7.1). Added an additional hepatic screening plot.
- Updated hypersensitivity analyses for immediate and nonimmediate events to be in line with adult safety analyses (Section 6.13.7.3).
- Added CDI-2 analysis to suicidal ideation/behavior and depression (Section 6.13.7.7).
- Removed language surrounding per protocol analysis.
- Updated data snapshot and interim analysis language in accordance with the protocol amendments.

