To evaluate the effect of treatment with mirikizumab on height velocity at Weeks 12, 24, and 52	Observed height velocity by gender and age group will be calculated at baseline, Week 12, Week 24, and Week 52
To evaluate the effect of treatment with mirikizumab on weight throughout the trial	Change from baseline in weight (kg) at all study visits by gender and age group
To evaluate the effect of treatment with mirikizumab on pubertal development throughout the trial in appropriate patient groups	Hormone levels and/or other related clinical measures will be evaluated
To evaluate the effect of treatment with mirikizumab on improving	Change from baseline in 7-day average of Abdominal Pain (in past 24 hours) NRS score at Week 12 and Week 52
patient-reported outcome endpoints at Week 12 and Week 52	The proportion of patients with a NRS pain score ≥3 at baseline who achieve an improvement of ≥30% from baseline in 7-day average abdominal pain NRS score at Week 12 and Week 52
To evaluate histologic-endoscopic mucosal remission following	Proportion of patients with histologic-endoscopic mucosal remission at Week 12
mirikizumab treatment at Week 12 or Week 52	Proportion of patients with histologic-endoscopic mucosal remission at Week 52
	Histologic-endoscopic mucosal remission is defined as achieving both histologic remission and endoscopic remission. Histologic remission is defined in Section 6.10.1.
To evaluate the development of antimirikizumab antibodies and their effect	Proportion of patients who have treatment-emergent anti-drug antibodies (TEADA)
CCI	CCI

Abbreviations: NRS = numeric rating scale; PK = pharmacokinetic; PUCAI = Pediatric Ulcerative Colitis Activity Index.

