		response	reduction in baseline PUCAI score of ≥20	missing.
		1	points.	8

Measure	Description	Variable	Derivation / Comment	Definition of Missing
	CCI			
Histo-Endo	Combined histology and endoscopic endpoints.	Histologic-endoscopic mucosal improvement Histologic-endoscopic	Histologic improvement and endoscopic remission. Defined as achieving both histologic	Missing if any component of the definition is missing. Missing if any component of the
		mucosal remission	remission and endoscopic remission	definition is missing.
CRP	C-reactive protein (CRP) is a biomarker of inflammation.	CRP	Lab value. May be transformed if needed.	Single lab value. Missing if missing.
Fecal calprotectin	Fecal calprotectin is used as a biomarker of intestinal inflammation in clinical practice.	Fecal calprotectin	Lab value. May be transformed if needed.	Single lab value. Missing if missing.
Growth and Pubertal Assessments	Occipital head circumference	Head circumference	Occipital head circumference measurements will be performed on patients less than 3 years of age at baseline. Measurements will be taken at baseline and then approximately Q12W thereafter, until the patient reaches the age of 3 years.	Data will be missing for patients who are 3 years or older at entry. Missing if missing.
	Change from baseline in height (cm)	Height CFB	Change from baseline in height (cm) at all study visits. Height is measured 3 times at all visits, height at each visit is calculated	Missing if baseline height or height at visit is missing.

Measure	Description	Variable	Derivation / Comment	Definition of Missing
			using the average of the 3 measurements.	
	Change from baseline in weight (kg)	Weight CFB	Change from baseline in weight (kg) at all study visits.	Missing if baseline weight or weight at visit is missing.
	Height Z-score and percentile by sex and age will be calculated using the CDC growth data shown at: https://www.cdc.gov/nccdphp/dnpao/growthcharts/resources/sas.htm	Height Z-score Height Percentile	Observed height z-score and percentile by sex and age	Missing if height at visit is missing.
	This approach uses a Box-Cox transformation to calculate the height z-score and percentile of the normal distribution for the corresponding age and sex.			
	Height Percentile Change from Baseline	Height Percentile CFB	Change from Baseline is calculated as Present height percentile – Baseline height percentile	Missing if baseline height or height at visit is missing.

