	Weight Z-score and percentile by sex and age will be calculated using the CDC growth data shown at: https://www.cdc.gov/nccdphp/dnpao/growthcharts/resources/sas.htm This approach uses a Box-Cox	Weight Z-score Weight Percentile	Observed weight z-score and percentile by sex and age	Missing if weight at visit is missing.
	transformation to calculate the weight z-score and percentile of the normal distribution for the corresponding age and sex.			
	Weight Percentile Change from Baseline	Weight Percentile CFB	Change from Baseline is calculated as Present weight percentile – Baseline weight percentile	Missing if baseline weight or weight at visit is missing.
	Observed height velocity by gender and age group. Age groups for which	Height velocity	Observed height velocity by gender and age group will be calculated at baseline	Data will be missing if either present height or previous height

Measure	Description	Variable	Derivation / Comment	Definition of Missing
	this will be summarized are 2 to <8, 8 to <12, and 12 to <18.		according to the following formula: (Present Height [cm] - Previous Height [cm])/Interval (months) Between Measurements × 12	is missing.
Assessment of Puberty	Total testosterone levels will be collected from male patients ≥9 years of age. Estradiol levels will be collected from female patients ≥9 years of age, until the female begins menstruating. If the patient is 9 years of age and has already begun menstruation, estradiol levels will not be required.	Hormone level	Total testosterone levels for male patients ≥9 years of age and estradiol levels for female patients ≥9 years of age, until the female begins menstruating.	Missing if patients are less than 9 years old or if date of onset of menstruation for females if exists. Missing if missing.
EIMs	Extraintestinal manifestations (EIMs) are collected using the	Baseline EIMs	EIMs ongoing at first dose of study treatment.	No Imputation.

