	PUCAI clinical response	Proportion for each weight/treatment	mITT	Weeks 12 and 52
		dose group along with the 95%	mITT who achieve PUCAI	Week 52
		2-sided CI with NRI and as observed.	clinical response at Week 12	
	PUCAI CFB	Descriptive statistics and 95% CI for	mITT	Weeks 12, 24, 36, and 52
		mean with mBOCF and as observed.		

		Analysis Method	Population	
Measure	Variable	(Section 6.1.3)	(Section 6.1.1)	Time Point(s)
Height	Height Velocity	Descriptive statistics and 95% CI for	mITT, by gender and age	Weeks 12, 24, and 52
	II : 14 CED	mean.	group	W 1 12 24 152
	Height CFB	Descriptive statistics and 95% CI for mean.	mITT	Weeks 12, 24, and 52
	Height Percentiles CFB	Descriptive statistics and 95% CI for mean.	mITT	Weeks 12, 24, and 52
Weight	Weight CFB	Descriptive statistics and 95% CI for mean.	mITT	At each scheduled visit.
	Weight Percentiles CFB	Descriptive statistics and 95% CI for mean.	mITT	Weeks 12, 24, and 52
Occipital head circumference	Head circumference	Descriptive statistics and 95% CI for mean.	mITT only on those patients less than 3 years at baseline	At all applicable visits (Week 12 + Q12W)
Puberty Development	Testosterone CFB	Descriptive statistics and 95% CI for mean.	mITT – males who are 9 years or older	Weeks 12, 36, and 52
	Estradiol CFB	Descriptive statistics and 95% CI for mean.	mITT – females who are 9 years or older without the date of onset of menstruation.	Weeks 12, 36, and 52
Abdominal Pain NRS	Abdominal Pain NRS score CFB	Descriptive statistics and 95% CI for mean with mBOCF and as observed.	mITT, summarized by age group	Weeks 12 and 52
. The	CCI			Week 12 and 52
CCI			mITT	Weeks 12 and 52
Histopathology	Histologic Remission	Proportion for each weight/treatment dose group along with the 95% 2-sided CI with NRI and as observed.	mITT	Weeks 12 and 52
	Histologic Improvement	Proportion for each weight/treatment dose group along with the 95% 2-sided CI with NRI and as observed.	mITT	Weeks 12 and 52

		Analysis Method	Population	
Measure	Variable	(Section 6.1.3)	(Section 6.1.1)	Time Point(s)
	Histologic-Endoscopic	Proportion for each weight/treatment	mITT	Weeks 12 and 52
	Mucosal Improvement	dose group along with the 95%		
		2-sided CI with NRI and as observed.		
	Histologic-Endoscopic	Proportion for each weight/treatment	mITT	Weeks 12 and 52
	Mucosal Remission	dose group along with the 95%		
		2-sided CI with NRI and as observed.		

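### SAP Table AMBU.6.5 omits the gender and age split that the weight endpoint requires, and gives percentile change but no row for the height and weight z-scores already derived

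*SAP*

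**What the plan says.** **Endpoints.** Protocol Table AMBU.2 and SAP Table AMBU.4.2 name height velocity and weight as secondary growth objectives. Both word the weight endpoint identically: "Change from baseline in weight (kg) at all study visits by gender and age group".

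**Derivations.** SAP Table AMBU.6.4 defines raw change in height and weight, percentile change, raw height velocity, and standardised scores from CDC growth data: "Observed height z-score and percentile by sex and age" and "Observed weight z-score and percentile by sex and age". The SAP revision history shows that this was deliberate in Version 2: "For growth, added definitions for change from baseline (CFB) in height, CFB in weight, and height/weight z-scores and percentiles".

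**Analyses.** SAP Table AMBU.6.5 has five rows for height and weight:
- Height Velocity, whose population cell begins "mITT, by gender and age" and continues to group
- Height CFB
- "Height Percentiles CFB"
- Weight CFB
- "Weight Percentiles CFB"

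The last four give mITT alone as the population.

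**Protocol commitment.** Protocol Section 9.1.6.2 states: "Age-specific z-scores for height velocity by gender and age group will be calculated for each patient". It gives the formula, refers to standard height velocity tables without naming them, and leaves the full details to the SAP.

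**The concern.** There are three gaps between what is defined and what is analysed.

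- The weight endpoint carries a gender and age split that its analysis row lacks. Patients are aged 2 to under 18, and expected kilogram gain over a year depends heavily on age and sex. A single mean mixes children for whom the same gain means different things.
- Height and weight z-scores are derived and then not used in any planned analysis. Percentile change is the only age-standardised change summary. Its mean depends on where each child starts, and it is least sensitive for very short or very light children.
- The velocity z-score was promised per patient, but the SAP neither derives nor analyses it.

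What is at stake is whether the secondary growth results can be read clearly, and whether they match their own definitions. The primary PK objective is not involved.

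**Working it through.** The plan states no effect size, SD or precision for growth, so there is no figure of its own to reproduce. The check is a comparison of text, followed by arithmetic for scale.

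**1. Endpoint against analysis row (weight).** Table AMBU.4.2 requires gender and age group; the Weight CFB row of Table AMBU.6.5 says mITT. This is not the table's shorthand, because the same column states a split or restriction wherever one applies: Height Velocity (gender and age group), Abdominal Pain NRS (age group), head circumference (under 3 years), hormones (sex, and 9 years or older). SAP Section 6.14 lists sex and age among subgroups that may be evaluated, so it does not commit to the split.

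**2. Derived against analysed (z-scores).** Table AMBU.6.4 derives height and weight z-scores. No row of Table AMBU.6.5 uses them.

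**3. Protocol against SAP (velocity z-score).** The SAP derives and analyses raw velocity only. It records no departure on this point, whereas the footnote to Table AMBU.6.1 openly flags a change to the protocol's safety population.

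**4. Percentile compression.** For a gain d from baseline z0, percentile change = 100 × [Φ(z0 + d) − Φ(z0)]. The baselines below are assumptions, with d = 0.5:

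| Baseline z | Calculation | Percentile points |
|---|---|---|
| 0 | 100 × (0.69146 − 0.50000) | 19.1 |
| -1 | 100 × (0.30854 − 0.15866) | 15.0 |
| -2 | 100 × (0.06681 − 0.02275) | 4.4 |
| -2.5 | 100 × (0.02275 − 0.00621) | 1.7 |

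From unrounded values, a gain from z = 0 counts 1.3 times as much as the same gain from z = -1 (19.15/14.99), 4.3 times as much as from z = -2, and 11.6 times as much as from z = -2.5.

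The two means can even differ in sign. Take two invented children, one moving from z = -2.5 to -1.5 and one from 0 to -0.25:
- mean z change = (1.00 − 0.25)/2 = +0.375
- mean percentile change = (6.06 − 9.87)/2 = -1.9 points

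**5. What the weight split can deliver.** Inputs: about 30 patients, at least 25 of them PK-evaluable (SAP Section 5.2); two sexes; three age groups (2 to <8, 8 to <12, 12 to <18, Table AMBU.6.4).
- Average cell size = 30/(2 × 3) = 5, or 25/6 = 4.2.
- The 95% CI half-width for a mean, in SD units, is t(0.975, n − 1)/√n. It is 1.24 SD at n = 5 and 0.37 SD at n = 30.

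**The case against.** The strongest reply is that growth is better covered than these gaps suggest.

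- **Height velocity**, the named height endpoint, is analysed by gender and age group at Weeks 12, 24 and 52. This stands. A reader might infer from the missing rows that growth is analysed only as raw and percentile change; that would be wrong.
- **Percentiles** are already standardised for sex and age and rise monotonically with the z-score. This also stands. A reader might infer that growth effects are hidden, but the documents do not support that: changes are compressed in the tails, not removed.
- **The size depends on the baseline chosen.** The 11.6-fold ratio needs a child at z = -2.5. At z = -1 the ratio is only about 1.3, and the documents do not say where patients will lie. This stands, which is why a range is shown.
- **The weight endpoint survives in Table AMBU.4.2**, SAP Section 6.1 plans to report the Section 4 endpoints in the CSR, and summaries by dose group (divided at 40 kg) partly separate ages. So the endpoint has not been withdrawn. But a programmer working from Table AMBU.6.5 would not produce it, and a weight band is not a sex-by-age split.
- **The study has no control arm** and plans no treatment comparisons, so no growth summary can isolate a drug effect. This is true of every scale; it limits the stakes without favouring percentiles.
- **Z-score change is not a defined endpoint**, so making it the lead growth summary would be a preference. This stands; it belongs beside the prespecified measures, not above them.

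**Conclusion.** The point holds as a minor matter of consistency and choice of scale. The mismatch in the weight row and the missing velocity z-score are discrepancies within and between the documents, and they need reconciling whatever one thinks of percentiles. Analysing z-scores that are already derived is an inexpensive improvement: it counts a 0.5 z gain equally for every child, and it standardises for age and sex without dividing about 30 patients into cells of about 5.

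The compression is a property of the normal scale. Its effect in this trial depends on baseline growth status, which the documents do not give, so the range from 19.1 down to 1.7 points is illustrative. The cell size assumes about 30 patients spread evenly over six cells; real cells will be uneven. Only the interpretation of the secondary growth results is affected, not PK or sample size.

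**What to change.** 1. In Table AMBU.6.5, mark the Weight CFB row by gender and age group, as Height Velocity already is, and say that the split is descriptive only.
2. Add rows for change from baseline in height z-score and in weight z-score beside the percentile rows, without ranking them above height velocity or kilogram change.
3. Either add the velocity z-score of protocol Section 9.1.6.2 to Tables AMBU.6.4 and AMBU.6.5 with a named reference table, or record that it has been dropped and why.

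Items 1 and 2 cost a few table rows, since the height and weight z-scores are already derived. Item 3 costs slightly more if the measure is kept: the SAP cites CDC data only for attained height and weight, so a velocity reference must be chosen. No new assessments are scheduled. Under SAP Section 6.1, a change to the analysis methods that does not touch a principal feature can be described in the CSR without a protocol amendment.

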6.1. Inclusion Criteria

Patients are eligible to be included in the study only if they meet all of the following criteria within the screening period, which is CCI [REDACTED], unless otherwise specified below:

Informed Consent

- [1] Have given assent (if appropriate) with parent/legal guardian signed informed consent approved by the ethical review board (ERB) governing the site.

Patient Characteristics

[figure not shown]
- [2] Male or female patients weighing >10 kg AND ≥ 2 and <18 years of age at the time of informed consent.

[2a]

CCI [REDACTED]

[2b]

CCI [REDACTED]

[3] Both the parent or legal representative and child (if capable) must agree to comply with the requirements of the protocol.

[4] CCI [Redacted]

Type of Patient and Disease Characteristics

[5] Have an established diagnosis of UC of ≥ 3 months in duration before baseline, CCI [Redacted]

[6] Have moderately to severely active UC as defined by a CCI [Redacted] within CCI [Redacted] before first dose of study treatment (baseline).

[7] Have evidence of UC extending proximal to the rectum CCI [Redacted]

Prior Medication Failure Criteria

[8] Patients must have an inadequate response to, loss of response to, or intolerance to at least 1 of the medications described in Criteria [8a] OR [8b]. **Documentation of dose, frequency, route of administration, and duration of the prior failed treatment is required.**

[8a] **Biologic-naive patients:** Patients who have an inadequate response to, loss of response to, or are intolerant to at least 1 of the following medications:

- Corticosteroids
 - Corticosteroid-refractory colitis, defined as signs and/or symptoms of active UC despite a CCI [REDACTED]

CCI [REDACTED]

CCI [REDACTED]

- Immunomodulators:
 - Signs and/or symptoms of persistently active disease despite at least 3 months' treatment with 1 of the following:

- Oral AZA CCI [REDACTED] or 6-MP CCI [REDACTED], or

CCI [REDACTED]

- History of intolerance to at least 1 immunomodulator CCI [REDACTED]

Discontinuation despite clinical benefit does not qualify as having failed or being intolerant to UC non-biologic therapy.

[8b] **Biologic/JAK inhibitor-experienced patients:** Patients who have an inadequate response to, CCI [REDACTED] to biologic therapy for UC (such as anti-TNF antibodies or anti CCI [REDACTED] antibodies) and/or to JAK inhibitors (such as tofacitinib), as described below.

Investigators must document an adequate trial of the medication.

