6.1.2. Baseline Definition

The baseline for variables collected as part of the old diary (including the SF and rectal bleeding (RB) components of the Modified Mayo) will be calculated from valid entries obtained prior to baseline endoscopy preparation (see Appendix 1). The baseline endoscopy component of the Mayo will use the endoscopic appearance of the mucosa at the screening endoscopy. For other efficacy, health outcome, and safety assessments, baseline is defined as the last non-missing assessment recorded on or prior to the date of the first study drug administration at Visit 2 (Week 0).

Baseline for safety analysis is described in the safety section.

Change from baseline will be calculated as the visit value of interest minus the baseline value. If a baseline value or the value at the visit is missing for a particular variable, then the change from baseline is defined as missing.

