6.1.3. Analysis Methods

For assessments of the binary efficacy endpoints and binary health outcomes, proportions for each weight class/treatment group along with the 95% confidence intervals (CIs) using the Wilson Score method (Wilson 1927; Newcombe 1998) will be provided. Non-responder imputation method will be used to estimate the percentage of patients achieving response across post-baseline visits.

Assessments of the continuous endpoints, descriptive statistics (n, mean, standard deviation [SD], minimum, first quartile, median, third quartile, and maximum) will be provided for each specified visit. Where appropriate, the mean and mean change from baseline with corresponding 95% CIs will be presented at each specified visit.

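### The hormone summaries have no age standard or pubertal-stage split, so mean raw change cannot by itself separate delayed from normal puberty

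*SAP*

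**What the plan says.** The objective, listed as secondary in SAP Section 4.2, is: "To evaluate the effect of treatment with mirikizumab on pubertal development throughout the trial in appropriate patient groups". Its endpoint allows hormone levels and/or other related clinical measures.

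Table AMBU.6.5 has two puberty rows, both at Weeks 12, 36 and 52:

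- **Testosterone:** change from baseline in mITT "males who are 9 years or older".
- **Estradiol:** change from baseline in mITT "females who are 9 years or older without the date of onset of menstruation".

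The method in both rows is "Descriptive statistics and 95% CI for mean". SAP Section 6.1.2 defines the scale: "Change from baseline will be calculated as the visit value of interest minus the baseline value". The SAP Revision History (Section 3) shows that Version 2 introduced it: "Changed estradiol and testosterone level analyses to be change from baseline". Eligibility runs to "<18 years of age at the time of informed consent" (Protocol Section 6.1).

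By default, results are shown by weight/treatment dose group plus all patients combined (SAP Section 6.1.1, Table AMBU.6.2). Age subgroups are optional (SAP Section 6.14). Protocol Section 9.4.3.2 limits hormone collection to patients not fully mature at Visit 1; the SAP testosterone row does not repeat this.

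**The concern.** Sex hormones rise unevenly through the years sampled. In a single-arm study with no planned comparison or covariate adjustment (SAP Section 6.2), the mean raw rise over 12 to 52 weeks is largely maturation, weighted by who enrolled. A low mean could reflect slow puberty or a sample with few children in mid-puberty. A high mean could hide children who lag behind their age.

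The SAP deals with this elsewhere. Height velocity is by gender and age group, abdominal pain is by age group, and Table AMBU.6.4 converts height and weight to sex- and age-specific z-scores and percentiles. The hormone rows get none of this. What is at stake is whether a stated secondary objective can be answered from the output the SAP commits to.

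**Working it through.** The plan gives no figure for the hormone analysis, so there is nothing to reproduce. It gives no hormone reference values, SDs, or split by age or sex. Both checks below therefore rest on assumptions.

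**1. Age mix alone, without units.** Let f be the share of patients in mid-puberty, their 52-week rise be 1 unit, and the rise in all others be o. Then pooled mean = f × 1 + (1 − f) × o.

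- With o = 0 and normal progression, the mean goes from 0.2 (f = 20%) to 0.8 (f = 80%) with no drug effect.
- Half-rate progression at f = 80% gives 0.5 × 0.8 = 0.40. Normal progression at f = 40% also gives 0.40.
- With o = 0.1, the same pair is 0.5 × (0.8 + 0.2 × 0.1) = 0.41 against 0.4 + 0.6 × 0.1 = 0.46.
- With o = 0.2, half rate at f = 80% gives 0.42, between the normal means of 0.36 (f = 20%) and 0.52 (f = 40%).

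The interval does not help. For 10 patients with changes of 0 or 1, four of them 1, the SD is √(0.24 × 10/9) = 0.516 and the 95% half-width is 2.262 × 0.516/√10 = 0.37. For 5 patients it is 0.68.

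**2. Assumed testosterone curves.** T(a) = 0.1 + P/(1 + exp(−(a − 13.5)/s)) ng/mL, with P = 4 or 6 and s = 0.6, 0.8 or 1.0 years. Ages are uniform within each band. Normal pace is T(a + 1) − T(a); half pace is T(a + 0.5) − T(a).

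With L(a) = ln(1 + exp((a − 13.5)/s)), the mean rise over a 3-year band from lo to hi with step d is (P × s/3) × [L(hi + d) − L(lo + d) − L(hi) + L(lo)]. For P = 4, s = 0.8:

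- Normal pace, 9-12: 1.0667 × (0.4287 − 0.0125 − 0.1427 + 0.0036) = 0.30.
- Half pace, 12-15: 1.0667 × (2.5789 − 0.2519 − 2.0177 + 0.1427) = 0.48.

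| P, s | Normal, 9-12 | Normal, 12-15 | Half pace, 12-15 | SD of normal rise, 9 to <18 | SD of normal rise, 12 to <18 |
|---|---|---|---|---|---|
| 4, 0.6 | 0.22 | 1.06 | 0.56 | 0.53 | 0.59 |
| 4, 0.8 | 0.30 | 0.92 | 0.48 | 0.41 | 0.45 |
| 4, 1.0 | 0.34 | 0.81 | 0.42 | 0.32 | 0.35 |
| 6, 0.6 | 0.34 | 1.59 | 0.83 | 0.79 | 0.88 |
| 6, 0.8 | 0.44 | 1.38 | 0.72 | 0.61 | 0.68 |
| 6, 1.0 | 0.51 | 1.21 | 0.63 | 0.48 | 0.53 |

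On all six curves, half pace at 12-15 exceeds normal pace at 9-12. The age-only SD within 12 to <18 is no smaller than over the whole range, so the SAP's existing older band does not remove the age mix.

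The ordering depends on the assumed centre. Repeating the formula with the centre at 14.0 or 14.5 keeps it on all six curves. At 13.0 it holds only for s = 0.6, and at 12.5 it holds on none. The curves show that the reversal can happen, not that it will.

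**3. Estradiol and menarche.** Table AMBU.6.4 makes estradiol missing once a menarche date exists, Section 6.1.2 then makes the change missing, and the row names no imputation. Girls who reach menarche leave the later means, so those who remain are selected towards slower progression.

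**The case against.** A reader might infer that pubertal safety is judged by one mean pooled over every child from 9 to under 18, and that a delayed child cannot be seen. The documents do not support that.

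- Estradiol is restricted to pre-menarchal girls, and Protocol Section 9.4.3.2 restricts collection to patients not fully mature at Visit 1. Contrasts that rely on boys aged 15-18 near an adult plateau are therefore weak evidence, and I do not use them.
- The default display is by weight/dose group, and weight is a partial proxy for age.
- Section 6.1.3 gives more than the mean: "minimum, first quartile, median, third quartile, and maximum) will be provided for each specified visit".
- The rows sit under secondary efficacy/health outcomes, with no threshold or test. Menarche date is collected, and height velocity by age group and height percentile change are reported.
- Part of the puberty section (Protocol Section 9.1.6.3) and the laboratory list (Protocol Appendix 2) are redacted. Whether hormones fall under the laboratory shift tables of SAP Section 6.13.4 cannot be seen.

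All of this stands, and it limits the claim. None of it supplies an age standard. Quartiles and extremes of raw change still cannot be read without age, the >40 kg group can mix mid-pubertal and late-adolescent boys, and the age subgroup is not a commitment.

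**Conclusion.** The point holds in limited form. The committed hormone summary is unstandardised change with no age- or stage-specific display, so by itself it cannot distinguish delayed puberty from age mix, and the secondary objective is left without a direct answer. This follows from the single-arm design and the wording of the rows. The sizes (0.42-0.83 against 0.22-0.51 ng/mL) rest on assumed logistic curves centred at 13.5 years and say nothing about this trial's actual age mix. The loss of estradiol data at menarche is a second, separate weakness.

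The documents do not show that the sponsor treats the mean as a safety verdict, or that no other output could reveal a delayed child. This is a worthwhile SAP correction to a descriptive secondary endpoint in a study sized for PK; it does not affect the primary objective.

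**What to change.** In Table AMBU.6.5:

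1. Make the main display a shift table, by sex: the number of patients below, within and above the laboratory's age- and sex-specific reference range at baseline and Weeks 12, 36 and 52.
2. Add a by-patient listing of hormone level, age and menarche date. Count girls who reach menarche during the study as having progressed, not as missing.
3. Keep mean raw change as supportive only, and do not rely on the 12 to <18 band to remove the age mix.
4. Reconcile the testosterone row with the maturity limit in Protocol Section 9.4.3.2.

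The cost is SAP wording, one table and one listing, with no new samples. There are two drawbacks. The laboratory must supply the ranges, which the documents do not give. Cells will also be small: with about 30 patients enrolled, a stratum of 5 at an assumed SD of 0.3 units (on the unit-free scale above) has a 95% half-width of 2.776 × 0.3/√5 = 0.37. That is why the individual listing is needed alongside the table.
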